3.7. Extent of Exposure

Descriptive statistics will be tabulated for the duration of treatment of both treatment groups, in weeks, during the respective active treatment phases, as of reference, up to the Week 96 visit, or in case of early discontinuation, last study medication intake. In addition, subject-years of exposure will be shown, derived as mean of treatment duration ((in weeks) x N) x 7 / 365.25.

Treatment duration (in weeks) is derived as follows:

$$(\text{End of phase} - \text{reference} + 1) / 7$$

Treatment interruptions will not be taken into account for the above definition.

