## 9.1.4. Extension Phase

Provided results from the DMC analyses or Week 24 interim analysis does not preclude (further) exposing subjects to D/C/F/TAF, subjects from the D/C/F/TAF arm will enter in the extension phase once they have completed their Week 48 visit. In addition, subjects in the control arm will receive the D/C/F/TAF tablet in the extension phase if, according to the investigator they will benefit from it and if all conditions are fulfilled (which includes adequate viral load results). Subjects from the control arm will be required to attend a switch visit at Week 52 to receive D/C/F/TAF. All subjects in the extension phase will have to attend visits every 12 weeks up to Week 96. As from Week 96, all subjects are offered the possibility to continue D/C/F/TAF treatment, if they wish and if they continue to benefit from it, until D/C/F/TAF becomes commercially available and is reimbursed, or can be accessed through another source in the country where he/she is living, or until the sponsor terminates clinical development. After Week 96, subjects should attend visits every 6 months. The time window for these visits is  $\pm 7$  days of the protocol-specified visit date.

Subjects from the control arm must have a Week 52 visit (switch visit) to allow providing D/C/F/TAF to subjects likely to benefit from it, based on the investigator's medical judgment. No investigations are foreseen during this visit, except for a blood sample collection to determine plasma HIV-1 RNA for those subjects that had HIV-1 RNA  $\geq$ 50 copies/mL at Week 48 and at the subsequent unscheduled visit. Information on concomitant medications, adherence and any AEs are to be collected during that visit.

In the extension phase, the following evaluations are to be completed and documented at each visit (except for the Week 52 switch visit).

- Review of AEs and changes in concomitant medications.
- Symptom-directed physical examination (physical examination for which symptoms have been reported by the subject) as needed at Weeks 60, 72, 84, 96 and every 6 months after Week 96.
- Vital signs measurement (blood pressure and pulse) and weight.
- Midstream urine sample collection for the following laboratory procedures:
  - Urinalysis and urine chemistry (see also Section 9.1.2.1).

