2.5. Visit Windows

2.5.1. Trial Phases

Phases will be constructed for each subject as follows for adverse events, concomitant therapies, and for the determination of the worst-case/toxicity/change in the cross-tabulations.

Trial phase	Start date	End date
Screening	Minimum of Date of signing the informed consent and Date of the screening visit	1 day before start of treatment
Comparative Treatment Phase	Date of the first intake (after randomization)	
For initial D/C/F/TAF subjects, in order of priority:
 
 - Week 48 visit date; if missing then - Projected Week 48 visit date, where projected Week 48 visit date = baseline visit date + (7 *48) 
For late switchers: Date of first D/C/F/TAF intake-1 day
 
In case of withdrawal use:
 
 - Minimum(last intake date of study drug, study withdrawal date) + 2 days
Extended Treatment Phase (Extension)	Last Date of Comparative Treatment Phase +1 day	
 - Week 96 visit date; if missing then - Projected Week 96 visit date, where projected Week 96 visit date = baseline visit date + (7 *96) 
In case of withdrawal use:
 
 - Minimum (last intake date of study drug, study withdrawal date) + 2 days
Follow-up	End of last treatment phase +1 day	Trial termination date for all groups (date of last contact)

Data up to each subject's Week 96 visit are in scope for this analysis, DXA data (DP domain) up to Week 96 visit+28 days, and if applicable, any (confirmatory) viral load or genotype/phenotype results immediately subsequent to Week 96 (up to 6 weeks).

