2.9. Reference

For Initial D/C/F/TAF group, reference is the comparative treatment phase baseline as in Week 48 analysis. For the late switch group two references will be used: (1) comparative treatment baseline will be used as reference for the period up to the switch; (2) the last value prior to the switch will be used as reference for the extended treatment phase.

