3.6. Treatment Adherence

Treatment adherence based on drug accountability will be summarized by means of descriptive statistics and frequency tabulations. Cumulative treatment adherence will be calculated from baseline through Week 96 for the Initial Switch to D/C/F/TAF arm; from baseline to the switch, and again from the switch to Week 96 for the Late Switch to D/C/F/TAF arm. Cumulative treatment adherence will be determined (derivation i).

The following parameters are derived:

Amount to be taken through switch/Week 96 = (number of days since start of treatment/switch \times number of tablets to be taken per day).

Number of days since start of treatmentswitch is based on (whichever comes sooner):

- last study medication intake (if available) or, in case subject discontinued and last study medication intake is missing, the last visit date prior to withdrawal will be used.
- Switch/Week 96 visit date

In addition (derivation ii), the cumulative treatment adherence up to time point where not more than one bottle is missing, or if available, up to switch/Week 96, whichever comes sooner, will be calculated.

Actual amount taken = (number of tablets dispensed – number of tablets returned), summed over time points up to the time point of interest.

Level of adherence = (actual amount taken / amount to be taken) × 100%

Treatment adherence is defined as:

- adherent: the level of adherence is >95%,
- non-adherent: the level of adherence is ≤95%.

Additionally, following categories of level of adherence will be defined:

- >95%
-]80%; 95%]
-]65%; 80%]
-]50%; 65%]
- ≤ 50%

Interruptions (for AEs) are not to be taken into account for the calculation of adherence, i.e. they will not be subtracted from the amount to be taken.

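### Read literally, the SAP 3.7 exposure formula starts late switchers' D/C/F/TAF time at a measurement that normally precedes the first dose by about four weeks

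*SAP*

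**What the plan says.** SAP 3.7 (Extent of Exposure) describes treatment duration in both groups "during the respective active treatment phases, as of reference, up to the Week 96 visit", or up to last study medication intake after early discontinuation. Its formula takes end of phase minus *reference* plus 1 day, divided by 7. Subject-years are "derived as mean of treatment duration ((in weeks) x N) x 7 / 365.25".

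*Reference* is a defined term. SAP 2.9 gives late switchers two: the comparative-phase baseline up to the switch, and after that "the last value prior to the switch will be used as reference for the extended treatment phase". For initial switchers it is the comparative-phase baseline throughout.

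Other sections date the late switchers' extension from the switch:

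- SAP 2.5.1 ends their comparative phase at "Date of first D/C/F/TAF intake-1 day" and starts the extended phase at "Last Date of Comparative Treatment Phase +1 day", which is the day of first D/C/F/TAF intake.
- SAP 3.6 computes the amount of drug to be taken from the "number of days since start of treatment/switch".
- The opening paragraph of SAP section 5 presents the late switchers' extended phase from the switch to Week 96.

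Protocol 9.1.4 says of the Week 52 switch visit: "No investigations are foreseen during this visit". The one exception is HIV-1 RNA in subjects who were at or above 50 copies/mL both at Week 48 and at the unscheduled retest.

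**The concern.** An exposure clock should start on a dosing date. The formula instead points to a term that the SAP defines through measurements. For most late switchers the last measurement before the switch is the Week 48 one, taken while they were still on bPI + FTC/TDF. The term also gives no single date, since the last value can fall on different days for different parameters.

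The late switchers' treatment duration and subject-years on D/C/F/TAF are at stake. These describe how much post-switch experience supports the long-term safety objective of the extension. A programmer who follows 3.7 and 2.9 to the letter would report control-regimen time as D/C/F/TAF time in that group. The initial switchers' start date would be right, because their reference is the Day 1 baseline.

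There is a smaller mismatch at the other end of the interval. The 3.7 sentence stops exposure at last intake for early discontinuers. The formula uses end of phase, which SAP 2.5.1 sets for withdrawals at the earlier of last intake and withdrawal date, plus 2 days.

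**Working it through.** The documents give no exposure or subject-years figure, so there is none to reproduce. The check applies the SAP's own formula with two different start dates.

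**Inputs**

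- Target days from SAP 2.5.2: Week 48 = Day 337 and Week 96 = Day 673. Both follow 7 × week + 1, which puts Week 52 at Day 365.
- Switch at Week 52 (Protocol 3.1; SAP 2.4).
- Last value before the switch at Week 48 (SAP 2.9 with Protocol 9.1.4).
- Planned arm sizes of 734 and 367 (SAP 1.2). The number who actually switched is not stated, so 367 is an upper bound.
- Visit windows of ±7 days (Protocol, Time and Events Schedule).

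**Late switcher completing Week 96, nominal dates**

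- Literal formula: 673 − 337 + 1 = 337 days; 337/7 = 48.14 weeks.
- From first D/C/F/TAF intake: 673 − 365 + 1 = 309 days; 309/7 = 44.14 weeks.
- Ratio: 337/309 = 1.091, an excess of 28 days or 9.1%.

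**Consistency check.** The late switchers' comparative phase runs from Day 1 to Day 364, which is 52.00 weeks. Adding the literal extension gives 52.00 + 48.14 = 100.14 weeks for someone on study for 673/7 = 96.14 weeks, so four weeks are counted twice. Starting at first intake gives 52.00 + 44.14 = 96.14.

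**Subject-years if all 367 switch and complete**

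- Literal: 367 × 337/365.25 = 338.6.
- From first intake: 367 × 309/365.25 = 310.5.
- Excess: 367 × 28/365.25 = 28.1.

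**Sensitivity of the percentage**

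| Case | Literal days | Days from first intake | Excess |
|---|---|---|---|
| Week 48 at +7 days, Week 52 at −7, Week 96 at +7 | 337 | 323 | 4.3% |
| Week 48 at −7 days, Week 52 at +7, Week 96 at −7 | 337 | 295 | 14.2% |
| Reference taken from a viral load retest at Week 51 (Day 358) | 316 | 309 | 2.3% |
| Exposure ends at Week 84 | 253 | 225 | 12.4% |
| Exposure ends at Week 72 | 169 | 141 | 19.9% |
| Exposure ends at Week 60 | 85 | 57 | 49.1% |

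**Pooled D/C/F/TAF exposure.** The 734 initial switchers followed to Week 96 contribute 734 × 673 = 493,982 days. The late switchers contribute 367 × 337 = 123,679 days literally, or 367 × 309 = 113,403 days from first intake. The ratio is 617,661/607,385 = 1.017, an excess of about 1.7%.

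**The case against.** The best defence is that the authors meant the switch date. The 3.7 sentence confines duration to the respective active treatment phases, and under SAP 2.5.1 the weeks between Week 48 and the switch belong to the comparative phase. SAP 2.7.1 describes D/C/F/TAF adherence as counted from reference, while 3.6 counts the same quantity from the switch, so the SAP does sometimes use the word loosely for the start of D/C/F/TAF. Also, if *reference* depends on the parameter, the last dosing-related record need not be from Week 48: the Time and Events Schedule has adherence and drug accountability at Week 52.

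Much of this stands. It makes the first-dose date the likely intention, and it means that the overstatement follows from one reading of the text and is not a certain result. It does not rescue the formula. The formula names only *reference*, the one definition of that term is a measured value, and nothing in 3.7 sends the programmer to first intake. A word used in two senses inside a formula needs correcting.

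The limited-impact argument also stands. SAP 1.3 and 4.4.1 make the Week 96 analysis descriptive, SAP 5.4.2 plans adverse-event incidences, and subject-years appear only in 3.7. The +2 days are minor: they touch early discontinuers only, by at most two days.

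**Conclusion.** The point holds as a specification error in a descriptive output. As written, SAP 3.7 with 2.9 starts the late switchers' extension exposure at a measurement that normally dates from Week 48, in conflict with SAP 2.5.1, 3.6 and section 5. For a completer on nominal dates the excess is four weeks, or 9.1%. This assumes a literal reading, a Week 48 reference and a Week 52 switch. Visit windows move the figure between about 4% and 14%, and it is larger for those who stop early. The total of about 28 subject-years is a ceiling that assumes all 367 control subjects switch and complete.

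A reader might infer three stronger things that the documents do not support:

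- **That exposure will certainly be overstated by 9%.** *Reference* has no unique date, and other wording suggests that the switch was intended.
- **That reported safety rates will be too low.** The SAP plans no rate per subject-year. A rate that someone later built on these figures would be 1 − 309/337 = 8.3% too low in late switchers on nominal dates, but none is specified.
- **That all D/C/F/TAF exposure is materially inflated.** The start-date error is confined to late switchers and comes to about 1.7% when pooled.

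The Week 48 primary analysis is untouched.

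**What to change.** In SAP 3.7, replace *reference* in both the sentence and the formula with the start date of the period being summarised, as given in SAP 2.5.1:

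- Late switchers, extended phase: date of first D/C/F/TAF intake.
- Initial switchers, baseline to Week 96: date of first intake (Day 1).
- Initial switchers, extended phase shown alone: the start date of that phase.

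The wording should name the period's start date. A rule based on first intake of the phase's treatment would take the initial switchers' extended phase back to Day 1, because they were already on D/C/F/TAF.

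As a minor addition, end the interval at last study medication intake for early discontinuers, as the sentence already says, without the 2 days built into end of phase.

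The cost is a line or two of SAP text and the matching program change. SAP 2.5.1 and 3.6 already require the dates, so no new data are needed. Compared with a literal implementation, the stated late-switch exposure becomes about four weeks shorter per subject.

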3.8. Protocol Deviations

All major protocol deviations will be tabulated and listed by treatment arm and overall. The proportion of subjects with one or more major protocol deviation that led to exclusion from the per protocol analysis set ([Attachment 1](#)) will also be tabulated.

3.9. Concomitant Medications

Concomitant medications are defined as any therapy used on or after the same day as the first dose of study agent, including those that started before and continue on after the first dose of study agent. Combination drugs are split up into their respective compounds. When counting the number of ARVs at a specific time point or during a specific time period, the separate compounds of these combination drugs are counted

Concomitant therapies will be grouped as follows, using a list of dictionary derived terms provided as metadata. These groups will be tabulated (n, %) per treatment group and analysis phase:

- lipid lowering drugs
- antidiabetic drugs
- antihypertensive drugs
- drugs for cardiovascular disease
- antiosteoporotic drugs

4. EFFICACY

4.4. Analysis Specifications

4.4.1. Level of Significance

No formal statistical tests will be calculated. All results will be descriptive.

4.4.2. Data Handling Rules

Plasma viral load levels will be measured using the ROCHE COBAS[®] AmpliPrep/COBAS[®] Taqman[®] HIV-1 Test, v2.0 assay, which will be conducted by the central laboratory.

Imputation of left censored HIV-1 RNA values: viral load results recorded as “< 20 HIV-1 RNA copies/mL detected” and “< 20 HIV-1 RNA copies/mL not detected” will be scored at 19.

CD4+ cell count and HIV-1 RNA data collected on treatment (up to the last dose date of study drug) will be used in the analysis.

4.4.2.1. Data Handling for Late Switchers

Except for analyses by analysis time point or change from baseline, data (i.e., Protocol-defined virologic rebound through Week96, Snapshot at Week 96, TLOVR and Resistance analyses) from the Late Switch to D/C/F/TAF group will be presented in tables and figures from the reference onwards to Week 96.

4.5. Primary Efficacy Endpoint

4.5.1. Definition

The primary efficacy endpoint of this study was the proportion of subjects with protocol-defined virologic rebound cumulatively through 48 weeks. Thus, the analysis of this endpoint is not described in the Week 96 SAP.

4.5.2. Analysis Methods

Not applicable.

4.6. Major Secondary Efficacy Endpoints

- The proportion of subjects with protocol-defined virologic rebound based on the HIV-1 RNA ≥ 50 , ≥ 20 and ≥ 200 copies/mL threshold through 96 weeks;

- The proportion of subjects with virologic response and failure based on the 20, 50 and 200 copies/mL threshold at Week 96, as defined by the FDA Snapshot approach (4.6.1);
- The proportion of subjects with virologic response and failure based on the 20, 50 and 200 copies/mL at Week 96, as defined by the TLOVR algorithm (4.6.1);
- Time to virologic rebound up to Week 96
- The change from reference in CD4+ cell count
- The proportion of subjects with viral blip based on the HIV-1 RNA ≥ 50 and ≥ 200 copies/mL threshold through 96 weeks

4.6.1. Definitions

Virologic Rebound

Virologic rebound is defined as:

- subjects who show confirmed HIV-1 RNA $\geq 50/20/200$ copies/mL from the reference up to, and including Week 96,
- subjects who discontinued prematurely (irrespective of reason) for which the last available (single) HIV-1 RNA value on treatment was $\geq 50/20/200$ copies/mL.
- any subject with last available on-treatment HIV-1 RNA $\geq 50/20/200$ copies/mL at the study cut-off of Week 96 (i.e., any last viral load [re]test having occurred no later than 6 weeks after Week 96)

All other situations are considered non-rebounders.

Snapshot approach (applying 20/50/200 copies/mL as threshold)

The Snapshot approach will classify subjects into 3 outcome categories: “virologic success”, “virologic failure” and “No viral load data”. Several subcategories of the outcome will also be presented in the analysis and are shown below. The categories below are mutually exclusive such that a subject will be included in one (sub)category. If a subject discontinues in the time window but also has an HIV-RNA value in the time window then the viral load data will be used to classify the subject’s category.

- Virologic success:
 - Last available HIV RNA $< 20/50/200$ copies/mL in the Week 96 visit window (Week 90-102)
- Virologic failure:
 - Last available HIV RNA $\geq 20/50/200$ copies/mL in the Week 96 visit window (Week 90-102)
 - Virologic failure leading to discontinuation

- Discontinued due to other reason (i.e. other than AE/death or virologic failure) and last available HIV-RNA $\geq 20/50/200$ copies/mL
- No viral load data in the Week 96 visit window
 - Discontinued due to AE/death (subjects will be classified in this category if discontinued prior to Week 96 window regardless of HIV-RNA level)
 - Discontinued due to other reason (i.e. other than AE/death or virologic failure) and the last available HIV RNA $< 20/50/200$ copies/mL (or missing)
 - Missing data during the Week 96 visit window but on study

The following threshold criteria are considered:

- < 20 : HIV RNA below 20 copies/mL (target not detected or target detected)
- < 50 : HIV RNA below 50 copies/mL
- < 200 : HIV-RNA below 200 copies/mL

Imputations for missing values

The following imputation method is used to calculate **virologic response** at a given time point:

- observed case: subjects with a missing value are disregarded in the analysis for that time point.
- TLOVR: responders/non-responders are defined according to the FDA Time To Loss Of Virologic Response algorithm; a subject is considered a responder at a given time point if the applicable HIV-RNA criterion is fulfilled at that time point and at the subsequent time point; a subject is considered a confirmed non-responder at a time point in the following situations in order of precedence:
 - the subject (permanently) discontinued at that time point or before
 - the subject shows a 'rebound' HIV-RNA value (\geq threshold copies/mL) at that time point and the subsequent time point;
 - the subject shows a confirmed rebound at an earlier time point (irrespective of re-suppression of viral load)
 - intermittently missing values are considered as response if the immediately preceding and following visits demonstrated response; in case the subject had not reached the next visit yet, no imputation is performed for the missing time points, unless the subject had discontinued the trial.
 - Remark: in case multiple virologic response observations are available within the same time window, all observations are used to determine TLOVR-imputed response for that time window. In case the subject has not reached the next visit yet, this subject is left out of the analysis for the missing time points.

In addition, TLOVR outcome table at Week 96 will be presented.

Time to rebound: The time (in weeks) calculated from reference until the first rebound time point (time point before confirmation of rebound) up to Week 96 visit. Subjects never losing the response up to Week 96 visit will be censored at the end of the extended treatment phase.

Immunologic response: The change from reference in CD4+ count and CD4% at a given time point is defined as: (CD4+/CD4% at a given time point - reference CD4+/CD4%).

Subjects who discontinue will have their CD4 values after discontinuation imputed with their reference value, thus resulting in a 0 change (NC=F). Other (intermittent) missing values will be imputed using last observation carried forward (LOCF). Apart from imputed, observed data will also be presented.

For cases where no observation is available at the baseline date, the last available screening value will be taken.

Viral Blip: A viral blip is defined as any HIV-1 RNA value $\geq 50/200$ copies/mL preceded and followed by HIV-1 RNA $< 50/200$ copies/mL (a confirmed rebound does not constitute a Blip). All HIV-1 RNA viral load data from the reference point to lower limit of the Week 96 window will be used to classify Viral Blip.

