- q If the regular dosing time coincides with the study visit, study drugs can be taken on site during all visits up to Week 48 after all laboratory assessments which require fasting are performed.
- r Chemistry profile: AAG, ALP, AST, ALT, GGT, total bilirubin, direct and indirect bilirubin, total protein, albumin, CPK, bicarbonate, BUN, chloride, creatinine, glucose, phosphorus, potassium, sodium, uric acid, amylase (reflex lipase testing is performed in subjects with total amylase >1.5xULN). At baseline, Weeks 24, 48, and 96, analyses of glucose will be done as part of the fasting metabolic assessments and not as part of the chemistry profile.
- s Fasting metabolic profile (total, HDL and LDL cholesterol, triglycerides, glucose). If a subject has not fasted prior to the visit, the visit may proceed, but subject must return within 72 hours in a fasted state to have a blood draw for the metabolic assessments.
- t Hematology profile: hemoglobin, hematocrit, RBC count and parameters (mean corpuscular hemoglobin [MCH], MCH concentration and mean corpuscular volume), WBC count with differential (neutrophils, lymphocytes, monocytes, eosinophils, basophils), platelet count.
- u At screening only eGFRcr by Cockcroft-Gault, at other visits during the treatment and extension phase also eGFRcr by CKD-EPI.
- v Urine chemistry (quantitative measurement): creatinine, sodium, phosphate, glucose, protein, albumin. Urinalysis by dipstick: specific gravity, pH, glucose, protein, blood, ketones, bilirubin, urobilinogen, nitrite, leukocyte esterase, and microscopic analysis if needed.
- w Urine sample for selected renal biomarkers (including retinol binding protein [RBP] and beta-2-microglobulin) should be collected fasted. If the subject has not fasted prior to the visit, the visit may proceed, but the subject must return within 72 hours in a fasted state to provide a urine sample for renal biomarkers. Required on the ESTD visit if the last test was more than 12 weeks before the ESTD visit. Selected renal biomarkers are only performed up to Week 48.
- x If the HIV-1 RNA value is  $\geq$ 50 copies/mL a retest should be collected at a scheduled or unscheduled visit, 2 to 4 weeks after availability of the results (except for screening and baseline results).

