## 4.1. Inclusion Criteria

Each potential subject must satisfy all of the following criteria to be enrolled in the study.

- 1. The ability to understand and sign a written ICF, which must be obtained prior to initiation of study procedures.
- 2. Currently being treated with a stable ARV regimen consisting of a bPI (limited to DRV once daily with rtv or COBI, ATV with rtv or COBI, or LPV with rtv) combined with FTC/TDF only, for at least 6 consecutive months preceding the screening visit.

Subjects treated with the combination DRV + COBI + FTC/TDF and having completed the required visits in the GS-US-216-0130 study, and who are fulfilling the present protocol criteria, will be given the option to participate in this study.

Note: A change in pharmacokinetic booster (ie, rtv or COBI) will be allowed provided such a switch occurred no less than 1 month prior to the screening visit.

- 3. Documented evidence of being virologically suppressed while on a stable ARV regimen prior to screening: at least 1 plasma HIV-1 RNA measurement <50 copies/mL (or HIV-1 RNA undetectable by a local HIV-1 RNA test) occurring between 12 and 2 months prior to the screening visit while on the stable ARV regimen and have HIV-1 RNA <50 copies/mL at the screening visit.
  - A single viral load elevation of ≥50 copies/mL and <200 HIV-1 RNA copies/mL after previously reaching viral suppression ('blip') within 12 months prior to screening is allowed, provided a subsequent viral load measurement is <50 HIV-1 RNA copies/mL (or HIV-1 RNA undetectable by a local HIV-1 RNA test) prior to screening.
- 4. Screening eGFRcr  $\geq$ 50 mL/min according to the Cockcroft-Gault formula for creatinine clearance.
- 5. Absence of history of failure on DRV treatment and absence of DRV RAMs (including V11I, V32I, L33F, I47V, I50V, I54M, I54L, T74P, L76V, I84V, L89V), if documented historical genotypes are available.
  - If no historical genotype is available, the subject can be included, provided no previous failure on DRV treatment has been documented.
- 6. Normal ECG at screening (or if abnormal, determined by the investigator to be not clinically significant).
- 7. Screening hepatic transaminases (alanine aminotransferase [ALT] and AST) ≤5 x upper limit of the normal range (ULN).
- 8. Screening direct bilirubin  $\leq 1.5 \text{ x ULN}$ .
  - Subjects with documented Gilbert's Syndrome or hyperbilirubinemia due to ATV therapy may have total bilirubin up to 5 x ULN.

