#### 11.2. Sample Size Determination

A sample size of 1,100 subjects will yield 89% power if it is assumed that both treatment arms will have an equal rebound rate of 4% (confirmed HIV-1 RNA  $\geq$ 50 copies/mL up to, and including the upper bound of the Week 48 window or have discontinued prematurely, irrespective of reason, with the last available HIV-1 RNA  $\geq$ 50 copies/mL), that the noninferiority margin is 4%, and that the significance level of the test is at a 1-sided, 0.025 level.

Table 5 provides rebound rates from historical switch studies in virologically suppressed subjects and from the treatment-naïve study TMC114-C211 (ARTEMIS) in a subset of subjects (n=286) being virologically suppressed for at least 6 months (data available on file).

D/C/F/TAF (darunavir/cobicistat/emtricitabine/tenofovir alafenamide)

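### At the 20 copies/mL threshold, a single unconfirmed last value of 20 to 49 counts as virologic rebound, although no retest is required below 50

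*SAP*

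**What the plan says.** SAP section 4.6 lists among the major secondary efficacy endpoints "The proportion of subjects with protocol-defined virologic rebound based on the HIV-1 RNA" thresholds of 50, 20 and 200 copies/mL through 96 weeks. Section 4.6.1 defines rebound by three limbs, each applied at all three thresholds:

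- Limb 1: a confirmed value at or above the threshold, from reference up to Week 96.
- Limb 2: premature discontinuation with a single last on-treatment value at or above the threshold.
- Limb 3: a last available on-treatment value at or above the threshold at the Week 96 cut-off, meaning "any last viral load [re]test having occurred no later than 6 weeks after Week 96".

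Section 4.6.2 gives each group's rebound proportion an exact Clopper-Pearson 95% interval.

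The retest rule is in the protocol. Footnote x of the Time and Events Schedule says that from 50 "copies/mL a retest should be collected at a scheduled or unscheduled visit, 2 to 4 weeks after availability of the results". Protocol section 9.3 and item 12 of SAP Attachment 1 use the same trigger of 50. After Week 96, visits are every six months (SAP section 1.2).

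Two further rules bear on the 20 threshold. Under SAP section 4.4.2, results reported as below 20, whether or not virus was detected, "will be scored at 19". Under inclusion criterion 3 (protocol section 4.1), a subject must "have HIV-1 RNA <50 copies/mL at the screening visit".

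**The concern.** Limb 1 rests on confirmation. Limb 3 does not, but its wording allows a retest to replace the Week 96 value. At 50 and 200 the protocol requires that retest. At 20 to 49 nothing requires it, so the first reading is normally the last one inside the six-week cut.

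Classification at the 20 threshold then depends on timing. One reading of 24 copies/mL at Week 72, with values below 20 on either side, is not a rebound. The same reading at Week 96 is. Limb 2 does the same for a last value of 20 to 49 at discontinuation.

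The subject is still suppressed by the trial's own entry criterion, and 20 is the limit below which the SAP treats results as left-censored. The blip category cannot absorb these readings, because SAP section 4.6.1 defines blips only at 50 and 200.

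At stake is the meaning of one column of a major secondary endpoint. It would combine confirmed events with single low readings, and its confidence interval does not allow for that misclassification. The column is also called protocol-defined, although the protocol defines rebound only at 50 or above (sections 9.3, 11.1.1 and 11.5).

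**Working it through.** **The plan's own figure.** The documents state no expected rate for the 20 copies/mL endpoint. The only related figure is the power for the Week 48 test at 50 copies/mL: 4% rebound in both arms, a 4% margin, 734 and 367 subjects, and one-sided 0.025 (protocol section 11.2). The standard error is √[0.04 × 0.96 × (1/367 + 1/734)] = 0.01253. Power is Φ(0.04/0.01253 − 1.96) = Φ(1.233) = 0.891, which reproduces the stated 89%. This point does not touch that calculation.

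**Applying the definition.** Take a subject below 20 at every visit through Week 84 and at 30 copies/mL at Week 96.

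- Limb 1 is not met, because there are not two consecutive values of 20 or more.
- No retest is due, because 30 is below 50. The next scheduled visit is six months away, outside the six-week cut.
- Limb 3 is met at 20 but not at 50 or 200.

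If Week 84 had also been 20 or more, limb 1 would already apply. The point therefore concerns isolated last values only.

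**Illustrative size.** Assume a subject with no sustained rise has chance q of a reading of 20 to 49 at each scheduled visit, independently between visits. The documents give neither q nor the assay variability. Let A be the probability of no confirmed pair so far with the latest value below 20, and B the same with the latest value 20 to 49. Start with A = 1 and B = 0. At each visit:

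- new A = (A + B)(1 − q)
- new B = A × q

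After the last visit, limb 1 contributes 1 − A − B, limb 3 alone contributes B, and the total is 1 − A.

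The SAP section 2.5.2 table gives initial switchers 11 post-baseline visits (Weeks 2 to 96). Late switchers are analysed from the switch onwards (SAP section 4.4.2.1), which leaves four (Weeks 60, 72, 84 and 96).

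For four visits and q = 5%, A runs 0.9500, 0.9500, 0.9476, 0.9454 and B runs 0.0500, 0.0475, 0.0475, 0.0474. Limb 3 alone gives 4.74%, limb 1 gives 0.73%, and the total is 5.46%.

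| q per visit | Initial: limb 1 | Initial: limb 3 alone | Initial: total | Late: limb 1 | Late: limb 3 alone | Late: total |
|---|---|---|---|---|---|---|
| 3% | 0.87% | 2.89% | 3.76% | 0.26% | 2.91% | 3.17% |
| 5% | 2.37% | 4.66% | 7.03% | 0.73% | 4.74% | 5.46% |
| 8% | 5.84% | 7.01% | 12.85% | 1.82% | 7.31% | 9.13% |
| 10% | 8.87% | 8.35% | 17.22% | 2.80% | 8.91% | 11.71% |

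On the planned group sizes, limb 3 alone is about 21 to 61 of 734 initial switchers and 11 to 33 of 367 late switchers. These are upper figures, since not everyone randomised will reach Week 96. If a second reading of 20 or more were required, the limb 3 contribution would be B × q. At q = 5% in initial switchers that is 4.66% × 0.05 = 0.23%.

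**The case against.** - **Week 96 is descriptive.** SAP sections 1.3 and 4.4.1 rule out formal testing, so no decision turns on this column. That stands and limits the weight of the point.
- **Other planned tables help.** Snapshot at 20 separately shows last values of 20 or more in the Week 96 window, TLOVR at 20 requires two time points except at discontinuation, and the 50 and 200 columns sit alongside. That partly stands. A reader could suspect the cause of an excess at 20, but could not tell how many rebounders were unconfirmed.
- **Counting a single last value is a deliberate, conservative convention.** The protocol does so at discontinuation, at 50. This is fair at 50. At 20 the protocol has no counterpart and no retest rule.
- **A site may retest anyway.** It may. A second test inside the six weeks is neither required nor scheduled, but it is not excluded.

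Stronger readings are tempting, and the documents do not support them. A reader might take the totals in the table as the size of the fault. They include confirmed pairs (8.87 of 17.22 points for initial switchers at q = 10%), which this point leaves in place. A reader might also conclude that these values are only measurement noise. The documents give no assay variability, and some may be real low-level viraemia. Nor is limb 3 guaranteed to be clean at 50 and 200: a retest is required there, but it can be missed or fall after the six-week cut, and Attachment 1 item 12 provides for a missed one.

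**Conclusion.** The point holds at the 20 copies/mL threshold. Limbs 2 and 3 count one unconfirmed last value of 20 to 49 as rebound, while an isolated value at an earlier visit does not count. This follows from the text and needs no assumption.

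The size does need one. With q between 3% and 10% per visit and independence, limb 3 alone adds about 2.9 to 8.4 percentage points for initial switchers and 2.9 to 8.9 for late switchers. The increments are similar; the totals are lower for late switchers because they have fewer visits. Limb 2 was not quantified. Positive correlation between visits would move some of these subjects into limb 1.

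Confirmed values of 20 to 49, the Week 48 primary endpoint and its noninferiority conclusion are not affected. This is a modest, inexpensive correction to one column of a descriptive secondary endpoint.

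**What to change.** In SAP section 4.6.1, for the 20 copies/mL threshold only:

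- Keep limb 1: two consecutive on-treatment values of 20 or more.
- Keep limbs 2 and 3 for last values of 50 or more. Anyone counted at 50 or 200 is then also counted at 20, so the three columns stay nested. Requiring confirmation for every value at 20 would break this: a subject who discontinued with a single last value of 500 would be a rebounder at 50 and 200 but not at 20.
- Report subjects who qualify only through a single last value of 20 to 49 on a separate line for unconfirmed 20 to 49 values, outside the rebound proportion and its confidence interval.
- Drop the protocol-defined label at 20.

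Leave the 50 and 200 definitions unchanged. The cost is SAP wording and one derivation flag, with no new data. The small downside is that a true low-level rise first seen at the last visit appears on the unconfirmed line; it remains visible there.
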